4.7.3 Secondary Efficacy Endpoints

For analyses up to week 24 using the MMRM approach for continuous endpoints, only data collected up to week 24 will be included in the model.

4.7.3.1 Proportion of subjects achieving IGA success (defined as IGA 0 [clear] or 1 [almost clear]) at each visit up to week 24

A CMH test stratified by baseline IGA severity (3, 4) will be used to test the difference between each nemolizumab regimen and the placebo for the proportion of subjects achieving certain “success” at a given visit for ITT and PP populations. A 95% CI for the treatment difference will be calculated.

A bar chart and line plots will be produced over time for each treatment group to summarize the data (“responders”).

Sensitivity analysis: Sensitivity analyses will be performed as described in 4.7.1.3.

Subgroup analysis: Subgroup analyses will be investigated as described in 4.7.1.6.

Logistic regression will be used with response status as the dependent variable and treatment group, subgroup factor and interaction between treatment group and subgroup as independent variables. Odds ratios and the respective 95% CIs will be used for all subgroup comparisons. In addition, the p-values for the interaction of the treatment groups and the subgroups will also be provided, wherever appropriate.

4.7.3.2 Proportion of subjects achieving IGA success (defined as IGA 0 [clear] or 1 [almost clear]) and a reduction of at least 2 points at each visit up to week 24

This endpoint will be analyzed as described in section 4.7.3.1.

4.7.3.3 Percent change from baseline in EASI at each visit up to week 24

This endpoint will be analyzed as the primary efficacy endpoint using a MMRM approach for ITT and PP populations.

4.7.3.4 Absolute and percent change from baseline in weekly average of the peak and average pruritus NRS at each visit up to week 24

The following endpoints will be analyzed as the primary efficacy endpoint using a MMRM approach for ITT and PP populations.

- Absolute change from baseline in weekly average of the peak pruritus NRS at each visit up to week 24
- Percent change from baseline in weekly average of the peak pruritus NRS at each visit up to week 24
- Absolute change from baseline in weekly average of the average pruritus NRS at each visit up to week 24
- Percent change from baseline in weekly average of the average pruritus NRS at each visit up to week 24

The plots showing the changes over time within each treatment group will be provided.

Sensitivity analysis: Sensitivity analyses will be performed as described in 4.7.1.3 for percent change from baseline in weekly average of the peak pruritus NRS for Week 24 only.

Subgroup analysis: Subgroup analyses will be performed as described in 4.7.1.6 for percent change from baseline in weekly average of the peak pruritus NRS for Week 24 only using the same method as subgroup analysis for the primary efficacy endpoint.

4.7.3.5 Proportion of subjects with an improvement of weekly average pruritus peak NRS ≥ 4 from baseline to week 24

The response status will be analyzed using a CMH test as described in Section 4.7.3.1 for ITT and PP populations.

A detailed validation plan of the peak NRS responder analysis using anchor-based approach is included in Appendix 7.

4.7.3.6 Absolute and percent change from baseline in weekly average sleep disturbance NRS at week 24

The following endpoints will be analyzed as the primary efficacy endpoint using a MMRM approach for ITT and PP populations.

- Absolute change from baseline in weekly average sleep disturbance NRS at week 24
- Percent change from baseline in weekly average sleep disturbance NRS at week 24

The plots showing the changes over time within each treatment group will be provided.

4.7.3.7 Proportion of subjects achieving PCS success (defined as a weekly prorated rounded average PCS ≤ 1 [none - mild]) at week 24

The response status will be analyzed using a CMH test as described in Section 4.7.3.1 for ITT and PP populations.

4.7.3.8 Proportion of subjects with EASI-50, EASI-75 or EASI-90 (defined as achieving 50%, 75% or 90% reduction from baseline in EASI score) at each visit up to week 24

The following response status will be analyzed using a CMH test as described in Section 4.7.3.1 for ITT and PP populations.

- Proportion of subjects with EASI-50 (defined as achieving 50% reduction from baseline in EASI score) at each visit up to week 24

- Proportion of subjects with EASI-75 (defined as achieving 75% reduction from baseline in EASI score) at each visit up to week 24
- Proportion of subjects with EASI-90 (defined as achieving 90% reduction from baseline in EASI score) at each visit up to week 24

Sensitivity analysis using MI approach will be performed.

A histogram over time will be produced.

4.7.3.9 Absolute and percent change from baseline in SCORAD at week 24

The following endpoints will be analyzed as the primary efficacy endpoint using a MMRM approach for ITT and PP populations.

- Absolute change from baseline in SCORAD at week 24
- Percent change from baseline in SCORAD at week 24

4.7.4 Other Efficacy Endpoints

4.7.4.1 Disease severity scores (EASI, IGA, SCORAD, BSA, pruritus NRS, sleep disturbance NRS and PCS) at each visit including at follow up visit (week 28 and 32)

Data will be summarized descriptively by visit (Analysis population: ITT).

4.7.4.2 Change and percentage change from baseline in disease severity scores (EASI, SCORAD, pruritus NRS, and sleep disturbance NRS) at each visit

Data will be summarized descriptively by visit (Analysis population: ITT).

4.7.4.3 Change and percentage change in disease severity scores (EASI, SCORAD, pruritus NRS, and sleep disturbance NRS) from week 24/ET to follow up visits (week 28 and 32)

Data will be summarized descriptively by visit (Analysis population: ITT).

4.7.4.4 Proportion of subjects with an improvement of weekly average pruritus NRS ≥ 4 from baseline to each visit

The number and percentage of “responders” will be summarized by visit (Analysis population: ITT).

4.7.4.5 Proportion of subjects achieving PCS success (defined as a weekly prorated rounded average PCS ≤ 1 [none - mild]) at each visit including follow-up visits

The number and percentage of “responders” will be summarized by visit (Analysis population: ITT).

4.7.4.6 DPS at hour 2, 4, 8, 24, 48, and 72

Data will be summarized descriptively at each timepoint (Analysis population: ITT).

4.7.4.7 Monthly and total amount of TCS used during the treatment period (from baseline to week 24)

Data will be summarized descriptively (Analysis population: ITT).

Monthly and total amount of TCS used during the follow-up will be summarized separately.

Subjects who received rescue medication will be excluded from all TCS analyses.

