The medium potency TCS will not exceed an amount of approximately 100 g/month (Eichenfield 2015) and the low potency an amount of approximately 30 g/month. The TCS regimen will be adjusted during the study, according to the disease activity and tolerability by the subject: where lesions are cleared, TCS should be applied at a reduced frequency (e.g. from every other day to twice weekly) and then discontinued; they can also be applied at a reduced frequency or discontinued if judged to be medically necessary by the investigator (e.g. due to intolerance).

5.3.4.2 *Rescue therapies*

If deemed to be medically necessary by the investigator (i.e. significant worsening of signs and/or symptoms of AD), rescue therapies can be prescribed to the subjects at any time during the study. For the purpose of efficacy analysis, subjects receiving any rescue therapies will be considered as treatment failures. Whenever possible, efficacy and safety assessments (e.g. disease severity scores, laboratory tests) should be conducted immediately before administering any rescue therapies.

Rescue therapies could include higher potency and/or quantity of TCS, TCI, systemic treatment, phototherapy or combinational usage of different treatment modalities. Whenever possible, investigators should first use topical medications as rescue therapy, before escalating to systemic therapies. If subjects receive topical treatments or phototherapy as rescue therapy, study drug administration should be continued unless there is a safety concern according to the investigator's judgment (e.g. TCI are applied in large body areas other than the face, neck, or genital areas). If subjects receive a systemic rescue therapy (such as cyclosporine, systemic corticosteroids, methotrexate, mycophenolate mofetil, azathioprine or biologics) or TCI in large body areas, the study drug administration must be permanently discontinued (see Section 6.1.8.2).

Whenever possible, subjects should complete all study visits and assessments (including daily diaries), regardless of whether or not they have received rescue therapies and whether or not they have discontinued the study drug administration.

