7.1.2.3 Other efficacy endpoints

- Disease severity scores (EASI, IGA, SCORAD, BSA, pruritus NRS, sleep disturbance NRS and PCS) at each visit including at follow up visit (week 28 and 32)
- Change and percentage change in disease severity scores (EASI, IGA, SCORAD, pruritus NRS, sleep disturbance NRS and PCS) from baseline to each visit
- Change and percentage change in disease severity scores (EASI, IGA, SCORAD, pruritus NRS, sleep disturbance NRS and PCS) from week 24/ET to follow up visits (week 28 and 32)
- Change from baseline in each component of EASI score at each visit
- Proportion of subjects with an improvement of weekly average pruritus NRS ≥ 4 from baseline to each visit
- DPS at hour 2, 4, 8, 24, 48, and 72
- Monthly and total amount of TCS used during the treatment period (baseline to week 24)
- Time to rescue therapy
- Change from baseline to week 2 in 5-D itch scale total score
- If applicable, evaluation of the prurigo nodularis lesions over time

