9.1.2 Analysis populations

The following populations and evaluability criteria will be used to analyze the efficacy, safety, PK/PD and QoL endpoints. For the safety analyses, subjects will be analyzed as treated and for efficacy analyses subjects will be analyzed as randomized.

9.1.2.1 *Intent-to-Treat (ITT) population*

The ITT Population will consist of all randomized subjects. All efficacy endpoints will be analyzed based on the ITT population.

9.1.2.2 *Per-Protocol (PP) population*

The Per Protocol population will comprise all subjects in the ITT population who have no major protocol deviations that would have a significant effect on the efficacy of the study treatment. Only primary and selected secondary endpoints will be analyzed using PP population.

9.1.2.3 *Safety population*

The safety population will comprise all subjects in ITT population who receive at least one dose of study drug. Randomized subjects will only be excluded if there is a clear documented evidence that the subject did not receive any study drug injection. All safety data will be summarized based on the safety population.

9.1.2.4 *PK analysis population*

The PK analysis population will include all subjects in the safety population who provide at least one post-baseline evaluable drug concentration value.

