9.1.3 Imputation of missing data

The primary method to impute the missing values will be as follows:

Continuous Endpoints: To impute the missing values for continuous endpoints, Mixed-effect Model for Repeated Measures (MMRM) approach will be used for the primary and secondary endpoints.

In addition, Multiple Imputation (MI), Last-Observation Carried Forward (LOCF), Worst-Observation Carried Forward, Observed Case (OC), and Pattern-Mixture Model under missing not at random assumption will be carried out as sensitivity analysis for primary and selected secondary endpoints.

Binary Endpoints: All missing values will be treated as a Non-Responder for the binary endpoints.

LOCF, OC, MI and Pattern-Mixture Model under missing not at random assumption approaches will be used as sensitivity analysis to impute the missing values for the selected secondary endpoints.

Use of rescue therapy: All efficacy data, except OC, will be set to missing after rescue medication is used. In OC analysis, no observed data after subject has received rescue treatment will be excluded.

There will be no imputations for missing laboratory, and vital sign data. Further details on imputation of missing data will be provided in the SAP.

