4.4 Analysis Populations

The following analysis populations will be used to analyze the data.

Intent-to-Treat Population (ITT):

The ITT population will consist of all randomized subjects.

Per Protocol Population (PP):

The PP population will comprise all subjects in the ITT population who have no major protocol deviations that would have a significant effect on the efficacy of the study treatment. The PP population will be finalized prior to the final database lock.

Safety Population (SAF):

The safety (SAF) population will comprise all subjects in ITT population who receive at least one dose of study drug.

PK Analysis Population (PKAP):

The PK analysis population will include all subjects in the SAF population who provide at least one post-baseline evaluable drug concentration value.

The efficacy summaries and analyses will be based on the ITT population, which is based upon the Intention-to-Treat (ITT) principle. In the event that a subject is allocated the incorrect study treatment as per the study randomization list, subjects will be summarized and analyzed ‘as randomized’ (i.e., by randomized treatment group). In the event that a subject is stratified incorrectly, ‘randomized stratum’ will be used rather than ‘actual stratum’.

For the primary and selected secondary efficacy endpoints, a sensitivity analysis will be performed on the PP population to assess the robustness of the study conclusions to the choice of analysis population. Subjects will be included in the analysis according to the treatment ‘as randomized’.

The safety summaries and analyses will be based on the SAF population. Randomized subjects will only be excluded if there is clear, documented evidence that the subject did not receive any study drug injection. In the event that a subject is allocated the incorrect study treatment as per the study randomization list, subjects will be summarized and analyzed ‘as treated’ (i.e., by allocated treatment group).

Upon database release, protocol deviation and analysis population outputs will be produced and will be reviewed by Sponsor. An analysis population classification meeting will be arranged to discuss the outputs and to decide which subjects and/or subject data will be excluded from certain analyses. Decisions made regarding the exclusion of subjects and/or subject data from analyses will be made prior to database lock and unblinding and will be documented and approved by Sponsor.

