4.7.1.3 Handling of Missing Data

Use of rescue therapy: For the purpose of efficacy analysis, subjects receiving any rescue therapies will be considered as treatment failures. All efficacy data, except Observed Case (OC), will be set to missing after rescue medication is used. In OC analysis, observed data after subject has received rescue treatment will be included.

Diary data: If a subject has less than 4 diary entries in a week, the weekly prorated average scores will be set to missing.

The following methods will be used to impute the missing values:

Continuous endpoints: To impute the missing values for the primary analysis of continuous endpoints, Mixed-effect Model for Repeated Measures (MMRM) approach will be used for the primary and secondary endpoints (where applicable).

In addition, the following imputation approaches will be carried out as sensitivity analyses for primary and selected secondary endpoints to assess the robustness of findings. For sensitivity analyses, continuous endpoints will be analysed using analysis of covariance (ANCOVA) including terms of treatment group, baseline IGA severity (randomization strata), and the corresponding baseline value.

1. **Multiple imputation (MI) method under assumption missing at random (MAR):**

- a. Imputation phase: The missing data are filled in m times to generate m complete data sets. The selection of m depends on the required computing time. A reasonable range is 20 to 100 times, or may follow a rule of thumb that the number of imputations should be similar to the percentage of cases that are incomplete.
- b. Analysis phase: The m complete data sets are analyzed by using the same method as the corresponding primary analysis.

- c. Pooling phase: The results from the m complete data sets are combined for the inference.
2. **Last Observation Carried Forward (LOCF):** The last observed post-baseline value will be used to replace missing values for continuous variables. For questionnaire-based variables, LOCF will be applied to missing individual questions first, and the value of the total (or sub-scale) score will be derived based on the imputed individual questions.

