4.11 Changes in the Conduct of the Study or Planned Analysis

Changes in the conduct of the study may be instituted through a protocol amendment. Planned analyses will be revised as appropriate. Similarly, planned analyses may be changed as a result of planned blinded data reviews. Changes will be finalized prior to database lock.

The following endpoints are added:

- Secondary efficacy endpoint: Proportion of subjects achieving IGA success (defined as IGA 0 [clear] or 1 [almost clear]) and a reduction of ≥ 2 points at each visit up to week 24
- Other efficacy endpoint: Proportion of subjects achieving PCS success (defined as a weekly prorated rounded average PCS ≤ 1 [none - mild]) at each visit including follow-up visits

The following endpoint is revised:

- Secondary efficacy endpoint: Proportion of subjects with EASI-50, EASI-75 or EASI-90 (defined as achieving 50%, 75% or 90% reduction from baseline in EASI score) at each visit up to week 24 (at week 24 per the protocol)

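### SAP 4.7.4.7 labels TCS use as ITT but removes every subject given rescue medication, including their months before rescue, so the table describes a subset selected after randomisation

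*SAP*

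**What the plan says.** Protocol 7.1.2.3 lists monthly and total TCS use from baseline to week 24 among the other efficacy endpoints, with no exclusion. SAP 3.2.2.3 repeats it, limited to medium and low potency TCS, again with no exclusion. SAP 4.7.4.7 plans a descriptive summary, names ITT as its population, says follow-up use is summarised separately, and closes with: "Subjects who received rescue medication will be excluded from all TCS analyses".

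On the population, SAP 4.4 states: "The ITT population will consist of all randomized subjects". Protocol 9.1.2.1 states: "All efficacy endpoints will be analyzed based on the ITT population".

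On rescue, Protocol 9.1.3 states: "All efficacy data, except OC, will be set to missing after rescue medication is used". SAP 4.7.1.3 has the same rule: "All efficacy data, except Observed Case (OC), will be set to missing after rescue medication is used". Under Protocol 5.3.4.2, "rescue therapies can be prescribed to the subjects at any time during the study"; the trigger is significant worsening in the investigator's judgment, and a larger quantity of TCS is one of the permitted forms.

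**The concern.** Background TCS is adjusted to disease activity (Protocol 5.3.4.1) and may be tapered and stopped on improvement (Protocol 3.3). Use by arm is therefore context for the EASI result. Protocol 1.2 reports that TCS use fell with nemolizumab in the phase 1 study, so readers are likely to look at this table for a TCS-sparing signal.

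A reader who trusts the ITT label will take the arm comparison as protected by randomisation. It is not. Whether a subject appears depends on what happened after randomisation, on an event tied to worsening and sometimes to TCS use itself. If the arms differ in how many subjects are rescued, or in which ones, the remaining groups are no longer the randomised groups.

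**Working it through.** The plan states no figure for this endpoint, so there is nothing to reproduce. The check is a comparison of the texts followed by a count.

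**1. Label against rule.** ITT is all randomised subjects. The table holds all randomised subjects minus those given rescue medication. The two sets differ as soon as one subject receives rescue medication.

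**2. Specific rule against general rule, monthly use.** SAP 4.6 describes the weighing cycles. Month 1 combines the cream dispensed at baseline, week 1 and week 2. Months 2 to 6 start at weeks 4, 8, 12, 16 and 20. That makes six cycles to week 24. Take a subject whose first rescue medication falls in cycle k, and treat that cycle as missing:

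- after-rescue rule (SAP 4.7.1.3): cycles 1 to k−1 are kept;
- SAP 4.7.4.7: no cycle is kept;
- complete pre-rescue cycles lost: k−1, so 0 to 5 (for k = 5, four).

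**3. Total use.** A subject rescued before week 24 has no complete total under SAP 4.7.1.3 either, so for the total the two rules largely coincide. The difference lies in the monthly figures.

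**4. Illustration of the counts.** The documents give no rescue rate. Assume 50 subjects per arm (the planned number), a proportion p given rescue medication, rescue spread evenly over the six cycles and no other dropout. Mean pre-rescue cycles lost per rescued subject = (0+1+2+3+4+5)/6 = 2.5. Then:

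- excluded by SAP 4.7.4.7 = 50p
- pre-rescue cycles lost = 50p × 2.5, out of 6 × 50 = 300
- month 1 contributors: 50(1 − p) under SAP 4.7.4.7; 50(1 − p/6) under the after-rescue rule
- month 6 contributors: 50(1 − p) under both

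| Assumed p | Excluded | Cycles lost of 300 | Month 1, SAP 4.7.4.7 | Month 1, after-rescue rule | Month 6, both |
|---|---|---|---|---|---|
| 10% | 5 | 12.5 | 45 | 49.2 | 45 |
| 12% | 6 | 15 | 44 | 49.0 | 44 |
| 20% | 10 | 25 | 40 | 48.3 | 40 |
| 30% | 15 | 37.5 | 35 | 47.5 | 35 |
| 40% | 20 | 50 | 30 | 46.7 | 30 |

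The timing assumption matters. At p = 30% the loss is 0 cycles if all rescue falls in cycle 1 and 15 × 5 = 75 if all falls in cycle 6.

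The table shows how much pre-rescue data the rule discards under these assumptions. It says nothing about grams: that would also need TCS use by rescue status, which the documents do not give. The last column shows that the after-rescue rule removes the selection in early months but not in month 6.

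**The case against.** The best defence is measurement. Rescue may be a larger quantity of the same study cream, and tube weights may not separate background from rescue use. That stands as a reason to treat weights from rescue onward with caution. It does not reach earlier months, which hold no rescue cream, and it supports a labelled subset rather than an ITT label.

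A second defence is that ITT here names only the source population, and the exclusion is openly stated in the same section. The SAP does elsewhere show subsets under an ITT heading, such as time to discontinuation among those who discontinued (SAP 4.3.1). But that display is defined by its subset. The TCS endpoint is not, and a table carrying the ITT label would not show the restriction unless someone added it.

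Third, the practical effect is small. The endpoint is descriptive, rescue itself is reported on ITT as counts and as time to event (SAP 4.5.3.3, 4.7.4.8), and by-subject listings of TCS use and rescue allow a rebuild by hand. This stands and limits the weight of the point.

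A reader might also infer more than the documents support:

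- *All rescued subjects are dropped.* The sentence says medication, and SAP 4.5.3.3 separates rescue medications from procedures. A subject given phototherapy alone may stay in.
- *A rescue in follow-up erases the treatment period.* No time window is given, but follow-up use is summarised separately and SAP 4.7.4.8 counts rescue in the treatment period only. A per-period reading is natural.
- *SAP 4.6 presents TCS use without the exclusion.* Part of that section is blacked out, so this cannot be said.
- *An undeclared change was made.* SAP 4.11 does not list the exclusion, but its entries are endpoints, either added or under "The following endpoint is revised". The protocol leaves data-handling detail to the SAP, so the omission carries little weight.

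**Conclusion.** The point holds, at low stakes. As written, SAP 4.7.4.7 yields a table labelled ITT that describes subjects not given rescue medication, and it discards up to five complete pre-rescue months per excluded subject that the plan's own general rule would keep.

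It is tempting to conclude that the exclusion hides or creates a TCS-sparing effect. The documents do not support either. Subjects who go on to rescue might use more background cream than others, or less, and the arms might lose similar or different numbers. With no rescue rate and no expected TCS use given, any shift in grams would rest wholly on assumed inputs. Direction and size are therefore unknown, and the counts in the working illustrate data loss only. The primary EASI analysis does not depend on this table and is not affected.

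**What to change.** Replace the exclusion sentence in SAP 4.7.4.7 with text to this effect:

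> Monthly background TCS use (medium and low potency) is summarised in all ITT subjects, with data after first rescue medication set to missing as in 4.7.1.3, showing the number rescued and the number contributing per arm and month. Monthly and total use are also summarised as observed case in all ITT subjects regardless of rescue, based on weighed study TCS, with the number per arm whose rescue was a larger quantity of the study cream, because tube weights may not separate it. Any summary restricted to subjects without rescue medication is labelled a supplementary subset, with the number excluded per arm and rescue assessed within the period summarised.

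State also whether rescue procedures count.

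The cost is SAP wording and one or two extra tables. No new data are needed, because TCS returned by randomised subjects is already weighed (Protocol 6.3). There are two drawbacks. The after-rescue summary has fewer contributors in later months and stays selected there. The observed-case summary mixes background and rescue treatment once rescue has started.

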6.3 Other supplies

Syringes, needles, water for injection, peak flow meters, D-squames, and urine pregnancy tests (UPTs, with a sensitivity < 25IU/L) will be provided to the investigational sites to be used in this clinical trial.

TCS of medium potency (mometasone furoate 0.1% cream or hydrocortisone butyrate 0.1% cream) and low potency (hydrocortisone acetate cream or desonide 0.05% cream) will be provided to the investigational site for dispensation to subjects as background TCS therapy in this clinical trial. Subjects (including screen failure subjects) will be instructed to bring the used and unused TCS tubes back to the investigational sites at each visit. TCS returned by the randomized subjects will be weighted first, and destroyed by the sites after monitoring. All other returned TCS will be destroyed by the sites after monitoring.

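### SAP 4.7.4.7 labels the TCS-use summary ITT but drops every rescued subject, so valid pre-rescue months are lost and the arms shown are not the randomised groups

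*SAP*

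**What the plan says.** Both documents list monthly and total TCS use from baseline to week 24 under other efficacy endpoints (Protocol 7.1.2.3, SAP 3.2.2.3). The SAP counts medium- and low-potency TCS only. Protocol 9.1.2.1 states "All efficacy endpoints will be analyzed based on the ITT population", and both documents define ITT as all randomised subjects.

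SAP 4.7.4.7 plans a descriptive summary, names ITT as its population, and two sentences later adds: "Subjects who received rescue medication will be excluded from all TCS analyses".

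The general rule for rescue is narrower. Under SAP 4.7.1.3, efficacy data outside the observed-case (OC) analysis "will be set to missing after rescue medication is used". Protocol 9.1.3 has the same rule and adds for the observed-case analysis: "In OC analysis, no observed data after subject has received rescue treatment will be excluded". Neither section removes data collected before rescue.

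On what counts as rescue, Protocol 5.3.4.2 says: "Rescue therapies could include higher potency and/or quantity of TCS, TCI, systemic treatment, phototherapy or combinational usage of different treatment modalities".

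**The concern.** An ITT summary that omits everyone with a given post-randomisation event is not an ITT summary. The subjects left in each arm are those who did not need rescue, and that subset can differ between arms because of the drug.

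The endpoint makes this worse in one situation. A larger quantity of TCS is itself a form of rescue. A subject rescued with more medium- or low-potency TCS is removed for high use of the product being weighed. This does not apply to rescue by TCI, systemic drugs or higher-potency TCS.

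TCS is tapered as the disease improves (Protocol 3.3, 5.3.4.1). TCS use is therefore both a sign of drug effect and the co-treatment a reader needs when interpreting the EASI difference. A distorted TCS comparison would mislead on both counts.

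**Working it through.** **The plan's own figure.** The TCS endpoint has no sample size, test or expected value of its own. The plan's power statement (at least 90% with 50 per arm) concerns EASI. It reproduces, with a minimum of 0.927 over the candidate shapes if the 30-point difference is reached at 90 mg, and this issue does not touch it.

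**Step 1: data discarded.**

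Inputs: 200 randomised (Protocol 5.1) and six monthly intervals to week 24, the first combining the returns at weeks 1, 2 and 4 (SAP 4.6). Assumptions: first rescue falls evenly over the six intervals, and an interval containing rescue counts as post-rescue because its tube is weighed afterwards.

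- All intervals: 200 × 6 = 1,200.
- Lost per rescued subject under the general rule: (6+5+4+3+2+1)/6 = 3.5.
- Lost under SAP 4.7.4.7: 6, so 2.5 more.

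| Rescued | n | General rule, 3.5n | SAP 4.7.4.7, 6n | Extra loss, 2.5n | Month 1 dropped: n/6 vs n |
|---|---|---|---|---|---|
| 10% | 20 | 70 | 120 | 50 | 3.3 vs 20 |
| 20% | 40 | 140 | 240 | 100 | 6.7 vs 40 |
| 30% | 60 | 210 | 360 | 150 | 10 vs 60 |

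In month j the general rule has dropped n × j/6 subjects. By month 6 that is n, the same subjects as under SAP 4.7.4.7. The two rules differ most in month 1 and not at all in month 6.

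**Step 2: possible bias in month 1.**

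Let mP and mD be the month-1 means of never-rescued subjects on placebo and drug. Let pP and pD be the share, among those not rescued in month 1, who are rescued later. Let k be the later-rescued subjects' month-1 use divided by that of the never rescued. The difference under the general rule is

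d = mP[1 + pP(k−1)] − mD[1 + pD(k−1)],

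while SAP 4.7.4.7 shows mP − mD. All values are assumed: mP = 60 g and mD = 45 g, so SAP 4.7.4.7 shows 15 g; pP = 0.25 and pD = 0.10.

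| k | d (g) | 15 g compared with d |
|---|---|---|
| 0.75 | 56.25 − 43.875 = 12.375 | 15/12.375 = 1.212, 21% overstated |
| 1 | 60 − 45 = 15 | no bias |
| 1.25 | 63.75 − 46.125 = 17.625 | 1 − 15/17.625, 15% lost |
| 1.5 | 67.5 − 47.25 = 20.25 | 1 − 15/20.25, 26% lost |

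With pP = pD = 0.20, d is 14.25, 15, 15.75 and 16.5 g, running from 5% overstated to 9% lost. The chosen k values reach further above 1 than below it, so the table should not be read as evidence that loss is more likely.

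**Step 3: why a total cut off at rescue is not the remedy.**

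Take the same means in every month, k = 1, 25% and 10% rescued with even timing, and 2.5 months kept per rescued subject. Never-rescued totals are 6 × 60 = 360 g and 6 × 45 = 270 g, a difference of 90 g. Totals cut at rescue are

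- placebo: 0.75 × 360 + 0.25 × 2.5 × 60 = 307.5 g;
- drug: 0.90 × 270 + 0.10 × 2.5 × 45 = 254.25 g.

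The difference is 53.25 g, which is 41% less than 90 g, although k = 1 means rescued and never-rescued subjects use TCS at the same monthly rate. A truncated total is mechanically low in the arm with more rescue.

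**The case against.** The strongest defence is that the exclusion is explicit and has a sensible purpose. Rescue with extra TCS, TCI or systemic drugs contaminates the weights as a measure of background use. That justifies removing weights after rescue, which the general rule already does. It does not justify removing months weighed before any rescue, and the SAP gives no other reason.

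A second objection stands in part. Once post-rescue data are missing, a rescued subject's 24-week total is incomplete, and the plan has no rule for completing it. The conflict with the general rule is therefore clear for monthly use and weaker for the total.

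Third, other outputs help. Rescue counts (SAP 4.5.3.3) and time to rescue (SAP 4.7.4.8) show how many were rescued in each arm, though not their TCS use. By-subject TCS listings (SAP 4.6) do show it. Part of SAP 4.6 is redacted, so a further summary cannot be ruled out.

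Four stronger readings are tempting but not supported:

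- **That an observed-case analysis of TCS use has been lost.** Observed-case analyses are planned only for the primary and selected secondary endpoints (Protocol 9.1.3, SAP 4.7.1.3). SAP 3.2.2.2 defines the latter as the IGA, EASI and peak pruritus NRS endpoints. None was planned for TCS use.
- **That SAP 4.11 hides a protocol change.** That section itemises added and revised endpoints, and the protocol leaves further analysis detail to the SAP. The omission is minor.
- **That rescue during follow-up, or by phototherapy alone, removes a subject.** The sentence has no time limit, so the first is a literal reading, but a per-period reading is possible. SAP 4.5.3.3 separates rescue medications from procedures, so phototherapy alone may not trigger the exclusion.
- **That TCS sparing will be understated.** This needs higher TCS use among rescued subjects together with enough rescue on placebo, and the documents establish neither. Protocol 1.2 reports more atopic dermatitis events in each nemolizumab group in phase 2a. Protocol 1.3 says nemolizumab subjects were less likely to receive rescue under that study's criteria.

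**Conclusion.** The point holds for this one descriptive endpoint. As written, the summary is mislabelled ITT, discards pre-rescue months that the general rule keeps, and compares subsets selected after randomisation. For rescue by quantity of medium- or low-potency TCS, the selection depends on the outcome itself.

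The size is unknown. The 50, 100 or 150 lost subject-months rest on assumed rescue rates of 10%, 20% or 30% and even timing. The range from 21% overstatement to 26% loss rests wholly on assumed means, rescue rates and k, and includes no bias. The documents support neither a direction nor any effect on the primary inference. Severity is minor.

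**What to change.** Replace the exclusion sentence in SAP 4.7.4.7 with:

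> In all ITT subjects, by treatment group: (a) monthly medium- and low-potency TCS use, from complete dispensation-return intervals before the first rescue therapy in the treatment period, with the number contributing each month; (b) monthly and total use from all weighed TCS to week 24 regardless of rescue. The number rescued by week 24 will be shown with both.

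Do not report a total truncated at rescue. If the never-rescued summary is still wanted, keep it as supplementary and label it a subset, not ITT. A line in SAP 4.11 would be tidy.

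The cost is one sentence and one extra table. The data are already planned: "TCS returned by the randomized subjects will be weighted first" (Protocol 6.3), and, whenever possible, "subjects should complete all study visits and assessments (including daily diaries), regardless of whether or not they have received rescue therapies" (Protocol 5.3.4.2).

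Each summary has a limit, which is why both are needed. In (a), fewer rescued subjects remain in later months, and a subject rescued in month 1 adds nothing. In (b), only weighed study TCS is counted, so steroid exposure after systemic or high-potency rescue can be understated.
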